4.3.5 Case Report Forms

Criteria for Forms Submission: Criteria for timeliness of submission for all study forms are detailed in the Forms Guide. Forms that are not entered into Advantage eClinical within the specified time will be considered delinquent. A missing form will continue to be requested either until the form is entered into Advantage eClinical[®] and integrated into the Data Coordinating Center's (DCC) master database, or until an exception is granted and entered into the Missing Form Exception File, as detailed in the Forms Guide.

Reporting Patient Deaths: Recipient death information must be entered into Advantage eClinical[®] within 24 business hours of knowledge of the patient's death. If the cause of death is unknown at that time, it does not need to be recorded at that time. However, once the cause of death is determined, the Death Form must be updated in Advantage eClinical[®].

Center for International Blood and Marrow Transplant Research (CIBMTR) Data Reporting: Centers participating in BMT CTN trials must register pre- and post-HCT outcomes on all consecutive HCTs done at their institution during their time of participation to the CIBMTR. Registration is done using procedures and forms of the Stem Cell Transplant Outcomes Database (SCTOD). (Note: Federal legislation requires submission of these forms for all US allotransplant recipients.)

BMT CTN 1904 enrollment must be indicated on the SCTOD pre-transplant registration form. Additionally, CIBMTR pre- and post-transplant Comprehensive Report Forms must also be submitted for all patients enrolled on this trial. CIBMTR forms will be submitted directly to the CIBMTR through routine CIBMTR mechanisms.

Weekly GVHD Monitoring: GVHD should be monitored in accordance with BMT CTN guidelines as specified in the Manual of Procedures. Patients should be assessed weekly until Day +100 post-transplant for GVHD. After Day +100, patients will be assessed at each follow-up visit through 12 months for the presence of GVHD. For scheduling, a target day range has been provided in **Table 11**.

Internal Data Monitoring

It is the responsibility of the site PI to ensure the validity of all patient data as well as the safety of all patients.

Data Monitoring and Auditing

The Data Safety and Monitoring Board (DSMB) for the BMT CTN will convene as per standard procedure to review serious toxicities and adverse events for the purpose of determining whether the trial should be modified or stopped. Triggers for referral to the DSMB are described in the Stopping Rules Criteria of **Section 5.3**. If the monitoring of the safety endpoints described in **Section 5.3** results in a trigger for consultation with the DSMB, the DSMB may make recommendations about whether or not to continue accrual.

Records

Any publication or presentation will refer to patients by a unique patient number and not by name to assure patient confidentiality.

4.3.6 Adverse Event Data

4.3.6.1 Definitions

Adverse Event (AE): An AE is any untoward medical occurrence in a patient administered an investigational product or has undergone study procedures and which does not necessarily have a causal relationship with this treatment. An AE can therefore be any unfavorable and unintended sign (including an abnormal laboratory finding), symptom, or disease that is temporally associated with the use of a medicinal (investigational) product, whether or not related to the medicinal (investigational) product.

An abnormality identified during a medical test (e.g., laboratory parameter, vital sign, ECG data, physical exam) should be defined as an AE only if the abnormality meets 1 of the following criteria:

1. Induces clinical signs or symptoms.
2. Requires active intervention.
3. Requires interruption or discontinuation of study medication.
4. The abnormality or investigational value is clinically significant in the opinion of the investigator.

Expectedness: An adverse event can be Expected or Unexpected

- **Expected adverse events** are those that have been previously identified as resulting from administration of the agent. For the purposes of this study, an adverse event is considered expected when it appears in the current adverse event list, the Investigator's Brochure, the

package inserts or is included in the informed consent document as a potential risk.

- **Unexpected adverse events** are those that vary in nature, intensity, or frequency from information in the current adverse event list, the Investigator's Brochure, the package insert, or when it is not included in the informed consent document as a potential risk.

Serious Adverse Event: A serious adverse event (SAE), as defined by per 21 CFR 312.32, is any adverse event that results in one of the following outcomes, regardless of causality and expectedness:

- **Results in death**
- **Is life-threatening.** Life-threatening means that the person was at immediate risk of death from the reaction as it occurred, i.e., it does not include a reaction which hypothetically might have caused death had it occurred in a more severe form.
- **Requires or prolongs inpatient hospitalization** (i.e., the event required at least a 24-hour hospitalization or prolonged a hospitalization beyond the expected length of stay). Hospitalization admissions and/or surgical operations scheduled to occur during the study period but planned prior to study entry are not considered SAEs if the illness or disease existed before the person was enrolled in the trial, provided that it did not deteriorate in an unexpected manner during the trial (e.g., surgery performed earlier than planned).
- **Results in persistent or significant disability/incapacity.** Disability is defined as a substantial disruption of a person's ability to conduct normal life functions.
- **Is a congenital anomaly or birth defect; or**
- **Is an important medical event** when, based upon appropriate medical judgment, it may jeopardize the patient and require medical or surgical intervention to prevent one of the outcomes listed above. Examples of such medical events include allergic bronchospasm requiring intensive treatment in an emergency room or at home; blood dyscrasias or convulsions that do not result in inpatient hospitalization, or the development of drug dependency or drug abuse.

Medical and scientific judgment should be exercised in deciding whether expected reporting is also appropriate in situations other than those listed above. For example, important medical events may not be immediately life threatening or result in death or hospitalization but may jeopardize

the subject or may require intervention to prevent one of the outcomes listed in the definition above (e.g., suspected transmission of an infectious agent by a medicinal product is considered a Serious Adverse Event). Any event is considered a Serious Adverse Event if it is associated with clinical signs or symptoms judged by the investigator to have a significant clinical impact.

4.3.6.2 Classification of Adverse Events by Severity

The severity refers to the intensity of the reported event. The Investigator must categorize the severity of each SAE according to the National Cancer Institute (NCI) CTCAE Version 5.0. For any term that is not specifically listed in the CTCAE scale, intensity will be assigned a grade of one through five using the following CTCAE guidelines:

5. Grade 1: Mild; asymptomatic or mild symptoms, clinical or diagnostic observations only; intervention not indicated
6. Grade 2: Moderate; minimal, local or non-invasive intervention indicated; limiting age-appropriate instrumental activities of daily living
7. Grade 3: Severe or medically significant but not immediately life-threatening; hospitalization or prolongation of hospitalization indicated; disabling; limiting self-care activities of daily living
8. Grade 4: Life-threatening consequences; urgent intervention indicated
9. Grade 5: Death related to AE

4.3.6.3 Attribution of the Adverse Event in Relation to the Study Drug - Treosulfan

The relationship of each reported event to the study treatment (Treosulfan) will be assessed by the Investigator; after careful consideration of all relevant factors such as (but not limited to) the underlying study indication, coexisting disease, concomitant medication, relevant history, pattern of the SAE, temporal relationship to any study treatment interventions and de-challenge or re-challenge according to the following guidelines:

Possibly, Probably, or Definitely Related: there is a reasonable possibility that the study treatment caused the event. A relationship of possibly, probably, or definitely related to the investigational product is considered related for the purposes of regulatory authority reporting.

Unlikely, or Not Related: There is no reasonable possibility that the investigational product caused the event. An unlikely or not related relationship to the investigational product is considered unrelated for the purposes of regulatory authority reporting.

4.3.6.4 Required Adverse Event Reporting Requirements

Adverse event reporting will be consistent with BMT CTN procedures (BMT CTN Administrative Manual of Procedures, Chapter 6). It is BMT CTN policy that AEs meeting reporting criteria must be reported even if the investigator is unsure whether a relationship exists between the adverse event and the use of study treatment.

Unexpected, serious adverse events (SAEs) will be reported through an expedited AE reporting system via Advantage eClinical. **Unexpected, life-threatening and fatal SAEs must be reported within 24 hours of knowledge of the event. All other unexpected SAEs must be reported within three business days of knowledge of the event.** Events entered in Advantage eClinical will be reported using NCI's Common Terminology Criteria for Adverse Events (CTCAE) Version 5.0.

Expected AEs will be reported using NCI's Common Terminology Criteria for Adverse Events (CTCAE) Version 5.0 at regular intervals as defined on the Form Submission Schedule, including calendar-driven case report forms (e.g., Toxicity and GVHD) or event-driven case report forms (e.g., Relapse/Progression, Infection, and Death). **Any expected life-threatening SAE not collected on another study form must be reported through the expedited AE reporting system via Advantage eClinical.**

The Data and Safety Monitoring Board will receive reports of all unexpected SAEs and pregnancies upon review by the BMT CTN Medical Monitor. Summary reports for all reported SAEs will be reviewed by the DSMB on a semi-annual basis.

4.3.6.5 Procedure in Case of Pregnancy

If a female patient becomes pregnant during the study dosing period or within 90 days from the Treosulfan infusion, the investigator should report within 24 hours through an expedited AE reporting system via Advantage eClinical. The expected date of delivery or expected date of the end of the pregnancy, last menstruation, estimated conception date, pregnancy result, neonatal data and other related information will be requested.

The investigator will follow the medical status of the mother, as well as the fetus, as if the pregnancy is an SAE and will report the outcome. Additional information regarding the outcome of a pregnancy (which is categorized as an SAE) is mentioned below.

- “Spontaneous abortion” includes miscarriage, abortion and missed abortion
- Death of an infant within 1 month after birth should be reported as an SAE regardless of its relationship with the study drug
- If an infant die more than 1 month after the birth, it should be reported if a relationship between the death and intrauterine exposure to the study drug is judged as “possible” by the investigator
- In the case of a delivery of a living newborn, the “normality” of the infant is evaluated at the birth
- Unless a congenital anomaly is identified prior to spontaneous abortion or miscarriage, the embryo or fetus should be assessed for congenital defects by visual examination

Information will be collected at the time of delivery/birth and 6 months and 12 months after birth. If the patient completes the final study follow-up prior to 12 months after birth, a final status should be reported following the final study visit.

4.3.6.6 Reporting Requirements to the FDA

The sponsor (Fred Hutchinson Cancer Center) assumes responsibility for IND safety reporting to the FDA and participating investigators, in accordance with regulations under 21 CFR 312.32. The following process will be followed:

Each reportable SAE received from the transplant centers will be evaluated by the BMT CTN Medical Monitor, who will assess the seriousness, expectedness, and the relationship to the investigational product. Any event determined to be a suspected unexpected serious adverse reaction (SUSAR) will be reported to the FDA as an IND safety report in accordance with regulations under 21 CFR 312.32 by the Sponsor or designee. Investigators involved in the study will be provided with an Investigational Safety Letter (ISL) notifying them of an event that meets FDA IND reporting criteria.

- SAEs will be reported by the study site PIs to the IND Sponsor and the BMT CTN Medical Monitor via Advantage eClinical per the reporting timelines.
- SAEs received will first be evaluated by the BMT CTN Medical Monitor, who will make a determination of whether the SAE constitutes a SUSAR.
- SAE determined to be a SUSAR will be reported by BMT CTN to the Fred Hutch Medical Monitor.
- SAEs identified by the BMT CTN Medical Monitor and/or Fred Hutch as SUSARs will be reported by Fred Hutch to FDA in an IND safety report in accordance with regulations under 21 CFR 312.32.
- The Fred Hutch Medical Monitor and BMT CTN Medical Monitor will review cumulative SAE data at regular intervals to monitor for new safety signals or events meeting IND safety reporting criteria.
- To make their determination of whether an event is a SUSAR, the BMT CTN and Fred Hutch Medical Monitors will assess the seriousness and expectedness of the event, as well as relationship to participation in the study.
- Fred Hutch or its designee will provide all study site PIs with a safety letter notifying them of an event that meets FDA IND Safety Reporting criteria. Study site PIs will be requested to provide written notification of safety reports to the IRB of record as soon as is practical, consistent with IRB requirements.

CHAPTER 5

5 STATISTICAL CONSIDERATIONS

5.1 Study Design

This is a prospective, multicenter phase II study designed to evaluate the outcomes of patients with BMFD undergoing HCT using Treosulfan-based conditioning. The primary endpoint is GVHD-free, Event-free survival (GEFS) at 1 year. The target enrollment is 40 patients transplanted using a Treosulfan-based conditioning.

5.1.1 Accrual

It is estimated that 48 months of accrual will be necessary to enroll the targeted sample size. Accrual will be reported by race, ethnicity, gender, and age.

5.1.2 Study Duration

Patients will be followed on trial for 12 months post-HCT for primary, secondary, and exploratory endpoints. Subsequent longer-term follow up on select endpoints will be available through the CIBMTR.

5.1.3 Randomization and Blinding

This is a single arm trial with no randomization and no blinding.

5.1.4 Primary Endpoint

The primary endpoint of the trial is GVHD-free, EFS (GEFS) at 1-year post-HCT using Treosulfan-based conditioning. Events contributing to this endpoint are specified in Section 3.1. The primary objective of this trial is to estimate the 1-year GEFS probability, using the Kaplan Meier method, along with 95% confidence intervals.

5.2 Sample Size and Power Considerations

Sample size justification is based on targeting acceptable confidence interval widths for the 1-year GEFS estimate. With n=40 patients, sample confidence intervals and their widths are provided in **Table 15** as a function of the observed GEFS, assuming complete follow up and based on exact Clopper-Pearson binomial confidence intervals. If GEFS is at least 85%, the lower confidence limit will rule out GEFS probabilities of 70% or less. In practice, if there is censoring of the primary endpoint prior to 1 year, Kaplan-Meier estimates will be used along with 95% confidence intervals. But we expect minimal to no censoring of the primary endpoint through 1 year, so the confidence intervals and their widths below should provide a good approximation.

Table 15: Sample 95% confidence intervals with n=40 as a function of observed GEFS.				
GEFS	95%	90%	85%	80%
95% CI	83-99%	76-97%	70-94%	64-91%

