 - b. For patients < 18 years old with a history of significant transfusions defined as ≥ 8 packed red blood cell transfusions per year for ≥ 1 year or have received ≥ 20 packed red blood cell transfusions (lifetime cumulative) will require formal hepatic iron measurement. In addition, patients with a prior history of hepatic iron overload will also require formal assessment for iron overload. Patients are excluded if:
 - i. Hepatic iron content ≥ 8 mg Fe/g dry weight by liver MRI using a validated methodology (such as T2* MRI or ferriscan) or liver biopsy per institutional practice.
8. Uncontrolled bacterial infection within 1 week of study enrollment. Uncontrolled is defined as currently taking medication with no clinical improvement or progression on adequate medical treatment.

9. Uncontrolled viral or fungal infection within 30 days of study enrollment. Uncontrolled is defined as currently taking medication with no clinical improvement or progression on adequate medical treatment.
10. Positive for HIV (human immunodeficiency virus).
11. Presence of clinically significant anti-donor HLA-antibodies per institutional practice.
12. Prior solid organ transplant.
13. Patients with prior malignancies except resected non-melanoma skin cancer or treated cervical carcinoma in situ.
14. Females who are pregnant or breast-feeding.
15. Females and males of childbearing potential who are unwilling to practice an effective method of contraception or agree to abstinence from the time of signing informed consent through 12 months post-transplant or off tacrolimus whichever is later.
16. Known hypersensitivity to Treosulfan or fludarabine.
17. Known life-threatening reaction (i.e., anaphylaxis) to Thymoglobulin that would prohibit use for the patient as this study requires use of the Thymoglobulin preparation of anti-thymocyte globulin (ATG).

Treatment Description:	Patients will be treated with a preparative regimen of Treosulfan (total dose 30-42 g/m ²), fludarabine (total dose 150 mg/m ²), and Thymoglobulin (total dose 6 mg/kg). GVHD prophylaxis will be with tacrolimus and methotrexate.
Accrual Objective:	The target sample size is 40 patients.
Accrual Period:	The estimated accrual period is 48 months.
Study Duration:	Patients will be followed for 1-year post-HCT.
Interim Analysis:	No interim analyses for efficacy or futility will be conducted.

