5.6 Analysis of Primary Endpoint

The probability of GEFS at 1 year will be estimated using the Kaplan-Meier method, along with 95% confidence intervals computed using a complementary log-log transformation.

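### Table 15 and the 85%/70% statement use exact binomial intervals, but the planned log-log Kaplan-Meier interval does not exclude 70% at 34/40 (a minor mismatch)

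*Protocol*

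**What the plan says.** The synopsis sets the size: "The target sample size is 40 patients". Section 5.2 justifies it by the width of the confidence interval for 1-year GEFS. Table 15 is titled "Sample 95% confidence intervals with n=40 as a function of observed GEFS", and its intervals are described as "assuming complete follow up and based on exact Clopper-Pearson binomial confidence intervals". Section 5.2 then draws one benchmark from the table: "If GEFS is at least 85%, the lower confidence limit will rule out GEFS probabilities of 70% or less".

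On the analysis method, section 5.2 says that "if there is censoring of the primary endpoint prior to 1 year, Kaplan-Meier estimates will be used along with 95% confidence intervals". It adds that little or no censoring is expected, so the table should approximate well.

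Section 5.1.4 names Kaplan-Meier as the estimation method without attaching a condition. Section 5.6 repeats this for the primary analysis and fixes the interval: Kaplan-Meier, "along with 95% confidence intervals computed using a complementary log-log transformation".

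**The concern.** Section 5.2 describes the precision of one interval and section 5.6 will report another. The two differ even when every patient is followed for the full year, which is the situation section 5.2 expects. Its remark about approximation therefore does not cover the gap: it concerns censoring, not the change of interval method.

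What is at stake is the one benchmark the protocol offers for reading the result. The threshold of 85% lies close to the 87% reported for the earlier cohort of 23 patients (section 1.2), so an observed result at or next to it is plausible. At exactly 34/40, a reader of section 5.2 would expect 70% to be excluded, and the section 5.6 analysis would not exclude it.

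**Working it through.** **Inputs.** n = 40 (synopsis, section 5.2); two-sided 95% level (Table 15); no censoring before 1 year (section 5.2, complete follow-up); z = 1.96.

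**Step 1: reproduce Table 15.** For x event-free patients out of n, the Clopper-Pearson limits are the 2.5% quantile of Beta(x, n−x+1) and the 97.5% quantile of Beta(x+1, n−x).

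| Observed | Exact 95% interval | Table 15 |
|---|---|---|
| 38/40 = 95% | 83.1–99.4 | 83–99 |
| 36/40 = 90% | 76.3–97.2 | 76–97 |
| 34/40 = 85% | 70.2–94.3 | 70–94 |
| 32/40 = 80% | 64.4–91.0 | 64–91 |

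All four columns of the table reproduce. The benchmark also holds on this basis: the lower limit at 34/40 is 0.7016, and P(X ≥ 34 | n = 40, p = 0.70) = 0.0238, which is below 0.025.

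**Step 2: the section 5.6 interval at 34/40.** Without censoring, the Kaplan-Meier estimate equals x/n and the Greenwood variance reduces to S(1−S)/n. The interval on the log(-log S) scale is S^exp(±z·s), with s = SE / (S·|ln S|).

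- S = 0.85
- SE = √(0.85 × 0.15 / 40) = 0.05646
- S·|ln S| = 0.85 × 0.16252 = 0.13814
- s = 0.05646 / 0.13814 = 0.4087
- exp(1.96 × 0.4087) = 2.228
- Lower limit: 0.85^2.228 = 0.6962
- Upper limit: 0.85^(1/2.228) = 0.9296

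The lower limit is 69.6%, so 70% is not excluded.

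**Step 3: the first count that excludes 70%.** At 35/40 = 87.5%, the same formula gives 0.7254 to 0.9460, which excludes 70%.

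**Step 4: the other columns, and the widths.**

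| Observed | Log-log interval | Width, exact (points) | Width, log-log (points) |
|---|---|---|---|
| 95% | 81.5–98.7 | 16.3 | 17.3 |
| 90% | 75.5–96.1 | 20.9 | 20.6 |
| 85% | 69.6–93.0 | 24.1 | 23.3 |
| 80% | 64.0–89.5 | 26.6 | 25.5 |

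The log-log interval is narrower at 80%, 85% and 90%, and about 1 point wider at 95%.

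**Step 5: how often it would matter.** Only X = 34 changes its reading.

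- True GEFS 85%: P(X ≥ 34) − P(X ≥ 35) = 0.607 − 0.433 = 0.174
- True GEFS 87%: 0.741 − 0.579 = 0.163

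**The case against.** The best defence is that the sentence is correct as written. Section 5.2 states its basis, exact intervals with complete follow-up, before giving the benchmark, and on that basis the benchmark holds. This stands: there is no arithmetic error in section 5.2. The fault is that the stated property is not a property of the interval that section 5.6 will report.

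A reader might go further and infer that the justification for 40 patients fails. The protocol does not support that. Its stated criterion is acceptable interval width, and the planned interval meets it about as well as the exact one.

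A reader might also see a loss of power, with the chance of excluding 70% falling from 74% to 58% if true GEFS is 87%. The figures are right, but they describe a test that the protocol does not contain. The primary objective is estimation (section 5.1.4), no success threshold is set, and section 5.3 plans no interim analysis for efficacy or futility. The drop is simply the probability of the single outcome 34/40.

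Two further objections carry some weight. The shortfall is 0.4 points, and at Table 15's whole-percent rounding 69.6 would still print as 70. Also, if complementary log-log is read literally as log(-log(1−S)), the lower limit at 34/40 is 72.4% and the benchmark holds. For a Kaplan-Meier interval, log(-log S) is the usual meaning, and the working uses it. That the answer turns on this choice is a reason to name the form.

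**Conclusion.** The mismatch is real and minor. Under the interval fixed in section 5.6, an observed GEFS of 85% gives a lower limit of 69.6% and does not exclude 70%; the threshold moves by one patient, to 35/40. At every other count the two methods agree about 70%. Conduct, sample size and safety monitoring are unaffected, and no prespecified decision depends on the difference.

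This rests on three assumptions: the log(-log S) form with Greenwood variance, exactly 40 patients analysed, and no censoring before 1 year.

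**What to change.** Keep section 5.6 and bring section 5.2 into line with it:

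1. Recompute Table 15 with the section 5.6 interval. The entries become 81–99% at 95%, 76–96% at 90%, 69.6–93.0% at 85%, and 64–89% at 80%. Keep the decimal in the 85% entry, because rounding would hide the point.
2. Replace the benchmark sentence with one to this effect: with complete follow-up, an observed GEFS of 87.5% or more (35/40) gives a lower 95% limit above 70%.
3. Name the log-log interval as the basis of the table, state the form as log(-log S), and drop the implication that Kaplan-Meier is used only when there is censoring.

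The cost is one small table and a few sentences, with a slightly less favourable stated threshold. The alternative is to use the exact interval whenever nobody is censored. That would preserve the 85% statement, but the analysis method would then depend on the data, which is debatable; aligning the planning text is simpler.
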